8.2 Sample size considerations

We will test our hypothesis that the BIPAS Alcohol intervention will increase parents' knowledge and decrease pro-sipping behaviors with 100 parents of 10-to-12-year-old children. We acknowledge that our trial is underpowered to detect small differences or control for multiple testing. One purpose of this feasibility study is to estimate effect sizes for powering a large-scale RCT. By piloting our intervention in two clinics, our study is designed to provide the data needed to lay this groundwork.

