3 OBJECTIVES

3.1 3.1 Study objectives

The purpose of this study is to evaluate the feasibility and preliminary effectiveness of BIPAS Alcohol, an intervention aiming to reduce pro-sipping beliefs, to encourage creation of clear, alcohol-specific rules, and to limit their provision of sips of alcohol to young adolescents.

3.2 3.2 Study outcome measures

Our primary outcome measure is changes in parents' self-reporting pro-sipping beliefs, attitudes, and practices at the end of the intervention period.

3.2.1 3.2.1 Primary outcome measures

For each participating parent, we will assess the change in composite score on an 8-item scale of self-reported pro-sipping beliefs, attitudes, and practices from baseline to 6 months (length of intervention). A four-point scale ranging from "strongly disagree" to "strongly agree" will be used, with higher values on the scale indicating a more pro-sipping belief system.

3.2.2 3.2.2 Other measures

No *a priori* secondary outcome measures.

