4 STUDY DESIGN

This study will evaluate the BIPAS Alcohol intervention with approximately 100 families. Parents will be randomized after enrollment into two groups: an intervention group and a waitlist-control group. Parents in the intervention group will begin receiving the intervention after enrollment, while parents in the waitlist-control group will receive the intervention three months after enrollment.

During the intervention period, all parents will receive text messages 2-3 times/week and online resources for three months about alcohol use and negative consequences in children, focusing on ways that they can create rules within the family environment to prevent alcohol use in children.

Parents in both groups will complete monthly surveys, and their child will complete one survey after three months. The parents in the intervention group will also receive a follow-up survey at 6 months. Parents in both groups will be asked if they would like to participate in an optional, follow-up qualitative interview about their experiences participating in the intervention.

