5.4 Treatment assignment procedures

5.4.1 Randomization procedures

We will use a coin flip to determine which group parents will randomly be assigned to after enrollment.

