8.4 Final analyses plan

We will use generalized linear mixed models to model change in parent attitudes and behaviors over time as a function of treatment arm and baseline characteristics. We will handle missing data on survey outcomes using multilevel multiple imputation. Parameter estimates generated from these secondary analyses will be used for refining the intervention and for power analyses in a subsequent grant proposal.

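### The declared primary outcome is tied to neither the hypothesis tested nor any primary analysis, and its 6-month time point has no concurrent untreated comparison

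*Combined protocol and SAP*

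**What the plan says.** The Synopsis and Section 3.2.1 declare a single primary outcome: each parent's change on an eight-item pro-sipping scale between baseline and month 6. Section 3.2.1 describes the scale as covering beliefs, attitudes and practices. Section 3.2.2 says that there are no a priori "secondary outcome measures".

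Section 8.1 states a hypothesis about knowledge and pro-sipping behaviors, and Section 8.2 commits to testing it: "We will test our hypothesis that the BIPAS Alcohol intervention will increase parents' knowledge and decrease pro-sipping behaviors". Section 8.2 then says: "We acknowledge that our trial is underpowered to detect small differences or control for multiple testing". It gives effect-size estimation for a larger trial as one purpose of the study.

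Section 8.4 contains the only analysis. Generalized linear mixed models will "model change in parent attitudes and behaviors over time as a function of treatment arm and baseline characteristics", with multiple imputation for missing survey data. It closes: "Parameter estimates generated from these secondary analyses will be used for refining the intervention and for power analyses in a subsequent grant proposal".

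On timing, Section 4 says: "Parents in both groups will complete monthly surveys". Sections 4 and 6.1 give the 6-month survey to the intervention group. Section 4 has waitlist parents receive the intervention from month 3.

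**The concern.** The declared outcome, the hypothesis to be tested and the planned model name three different sets of constructs, and no analysis is called primary. Someone following the plan cannot tell which estimate answers the study question or which one should size the later trial. Knowledge might improve while the eight-item score does not move, and the plan does not say how that result would be read.

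The time point adds a second difficulty. A change to month 6 measured only in treated parents is a before-after change, and it cannot separate the effect of the texts from time, repeated surveying or regression to the mean. The randomization then contributes nothing to the declared primary outcome.

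**Working it through.** **Outcome, hypothesis and model side by side**

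| Place | Construct | Time point and contrast |
|---|---|---|
| Synopsis, 3.2.1 | Eight-item pro-sipping score | Within-parent change to month 6; no arm contrast |
| 8.1, 8.2 | Knowledge; pro-sipping behaviors | None stated |
| 8.4 | Attitudes and behaviors; knowledge not named | Change over time by arm; no time point, alpha or named contrast; called secondary |
| 3.2.2 | No a priori secondary outcomes | Not applicable |

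The label in 8.4 has nothing to attach to: there are no secondary outcomes for it to analyse and no other analysis for it to be secondary to.

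**Timeline**

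- Months 0 to 3: the intervention arm receives texts and the waitlist arm does not. Both are surveyed monthly, so month 3 offers a randomized comparison with untreated parents, provided that the month-3 survey precedes the waitlist texts.
- Months 3 to 6: waitlist parents receive three months of texts, so by month 6 (3 + 3) they have had the full course.
- Month 6: a survey is stated for the intervention arm only. The Synopsis and Section 6.2 mention surveys for up to six months, so some later waitlist data may exist, but they would come from treated parents.

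Whether or not waitlist parents are surveyed at month 6, there is no concurrent untreated group at that point. Section 3.2.1 also describes six months as the length of the intervention, where Sections 4 and 6.1 give three; these statements need to be reconciled.

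**Sample size**

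The 100 parents in Section 8.2 cannot be reproduced, because no alpha, power, effect size, standard deviation or dropout is given. For illustration, assume two-sided 0.05, 80% power, no dropout and 50 per arm. The equal split is also an assumption: "We will use a coin flip to determine which group parents will randomly be assigned to after enrollment" gives it only in expectation. The detectable standardized effect is (1.960 + 0.842) × √(2/50) = 2.80 × 0.20 = 0.56. The admission of low power for small differences is therefore correct: power at a standardized effect of 0.2 is 16.9%.

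**Multiplicity, as illustration only**

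Assume two outcomes (knowledge and behaviors), one time point and two-sided 0.05 per test.

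- Success on either counts, independent outcomes: 1 − 0.95² = 0.0975.
- Success on either counts, correlation 0.5 (bivariate normal): 0.091.
- Favourable direction only: 1 − 0.975² = 0.049 if independent and about 0.045 at correlation 0.5, against 0.025 for a single test.
- Both must succeed: at most 0.05, so no inflation.

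**Cost of the two remedies**

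A Bonferroni split over two outcomes (0.025 each) raises the detectable effect to (2.241 + 0.842) × 0.20 = 0.62 and lowers power at a standardized effect of 0.5 from 70.5% to 60.2%. Naming one contrast and calling the others exploratory leaves the named contrast at 0.56 and 70.5%.

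**The case against.** The best defence is that this is a feasibility pilot and says so. It speaks of preliminary effectiveness, admits low power, discloses that multiplicity is not controlled, and intends its estimates for refinement and later planning. It states no alpha and no decision rule. A pilot need not have a contrast that decides it, and unadjusted estimates with intervals are acceptable. This stands, and it limits the point to specification and linkage. It does not remove the point, because Section 8.2 says that a hypothesis will be tested and because a pilot that supplies an effect size still has to say which effect.

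A reader might infer something stronger: that three domains at three monthly waves make nine tests, with a family-wise error of about 0.27 at correlation 0.5, and that the most favourable estimate will be carried into the next trial. The documents do not support this. Section 8.4 describes a longitudinal model, not separate tests at each wave. Knowledge is not in it. The behaviors of Sections 8.1 and 8.2 may be the practices already inside the eight-item composite. The hypothesis joins its two parts with *and*, which can be read as requiring both. Only favourable chance results would count as support, which halves the rates. Nothing says that the largest estimate will be chosen.

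It is also fair to object that a month-3 primary conflicts with the declared month 6. It does, unless the Synopsis and Section 3.2.1 are changed as well.

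**Conclusion.** The point holds as a gap in specification. The protocol contains no between-arm analysis of its one declared primary outcome, and at month 6 there is no concurrent untreated group to supply one. Both conclusions follow from the text and need no numerical assumption.

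The multiplicity effect is secondary and conditional. At an assumed two-sided 0.05, with either of two outcomes counting as success, the false-positive chance is about 0.09 at correlation 0.5 (0.098 if independent), or about 0.045 against 0.025 in the favourable direction. It vanishes if both outcomes must succeed, and the plan does not say which reading applies. The plan does not commit to reporting a chance finding as confirmation, so that charge should not be made.

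**What to change.** - **8.4:** name as the primary analysis the between-arm difference in the eight-item composite at month 3, from the planned mixed model, and delete the word secondary. Month 3 is the last wave before waitlist parents receive the intervention; state that this survey is completed before their texts begin. State the alpha and sidedness, or that inference is by estimation only.
- **Synopsis and 3.2.1:** change the primary time point to match, and keep the 6-month change in the intervention arm as descriptive. Without this edit the protocol would hold two conflicting primaries.
- **8.1, 8.2 and 3.2.2:** label knowledge, separate behavior measures and other time points as exploratory, reported as estimates with 95% confidence intervals. Replace the multiplicity sentence in 8.2 with a statement that one contrast is primary and the others are exploratory and unadjusted.
- **8.2 and 8.4:** state that the effect size for the later trial comes from the pre-named contrast.

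The cost is wording: no new data, no added participants and no loss of power on the named contrast. The downsides are that the stated primary time point changes and that the team can no longer claim support from knowledge or behavior results alone.

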Summary:	
Early alcohol socialization occurs within the family. Our multi-level, high-reach, low-intensity intervention to prevent early alcohol use capitalizes on the influence of providers, immunization timing, and pediatric guidelines that advise healthcare providers to give anticipatory guidance about early alcohol use. In conjunction, the intervention capitalizes on the power of technology to reinforce and expand upon pediatrician messages.
 
Our study seeks to understand the feasibility and effectiveness of a pilot intervention designed to prevent alcohol socialization through education of parents of rising 6th grade students.

Objectives:	
To evaluate the feasibility and preliminary effectiveness of an intervention aiming to improve parents' attitudes about child alcohol use.

	
Primary outcome measure: The change in parents' score from an 8-item scale of pro-sipping beliefs from baseline to post-intervention (6 months).

Sample:	Parents of rising 6 th grade students.
Phase:	Phase 0/1 (Intervention development)
Participant duration:	Parents will participate in a text-based intervention for three months and complete surveys for up to 6 months after study enrollment. Children will complete one survey 3 months after study enrollment.
Description of intervention:	BIPAS Alcohol is an intervention intended to prevent early onset alcohol use by educating parents of rising middle schoolers. Parents will receive information delivered via text message for three months.
Estimated time to complete	

enrollment: 6 months

Schematic of study design:

BIPAS Alcohol intervention

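### The effect size this pilot is meant to supply has no time point with an untreated comparison: the stated 6-month outcome falls after the waitlist arm starts the intervention

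*Combined protocol and SAP*

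**What the plan says.** **Purpose.** Section 8.2 states "One purpose of this feasibility study is to estimate effect sizes for powering a large-scale RCT". Section 8.4 adds "Parameter estimates generated from these secondary analyses will be used for refining the intervention and for power analyses in a subsequent grant proposal". The model in 8.4 is a generalized linear mixed model of change over time, with arm and baseline characteristics as predictors. It names no contrast and no time point.

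**Primary outcome.** The summary gives the change on an 8-item "scale of pro-sipping beliefs from baseline to post-intervention (6 months"). Section 3.2.1 gives the change for each parent on an "8-item scale of self-reported pro-sipping beliefs, attitudes, and practices from baseline to 6 months (length of intervention"). Section 3.2 places the outcome differently, as beliefs, "attitudes, and practices at the end of the intervention period".

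**Design.** Section 4 randomises about 100 families to immediate intervention or waitlist. The intervention group begins after enrolment, "while parents in the waitlist-control group will receive the intervention three months after enrollment". Sections 4 and 6.1 describe three months of messages.

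**Surveys.** Section 4 gives monthly surveys to both groups, with no stated end, and an additional 6-month survey to the intervention group. Section 6.1 repeats the latter. The summary says more generally that parents "complete surveys for up to 6 months after study enrollment", and Section 6.2 describes messages and monthly surveys for each parent over up to six months.

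**The concern.** An effect size for a later RCT is one of the products the plan promises. To be useful it must estimate the difference between parents who have had the intervention and comparable parents who have not. The randomised waitlist arm provides those untreated parents only until it starts the intervention at 3 months. The primary outcome is read three months after that.

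An analyst who follows the stated primary time point therefore has no randomised untreated comparison. A within-arm change over 6 months mixes any intervention effect with time trend, the child's ageing, repeated questioning and regression to the mean. A 6-month comparison between arms, if both are surveyed, sets two treated arms side by side. Either figure could be carried into the grant proposal as the effect size, and nothing in 8.2 or 8.4 points to the contrast that would serve.

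**Working it through.** The plan gives no SD, correlation, dropout rate, target effect or power figure, so there is no calculation to reproduce. The main check is to set the sections side by side.

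**Step 1. Who is untreated, and when** (Section 4 timing)

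| Months from enrolment | Intervention arm | Waitlist arm | Surveys |
|---|---|---|---|
| 0 to 3 | receiving | not yet started | monthly, both arms |
| 3 to 6 | finished, if the length is three months | receiving | monthly, end not stated |
| 6 | follow-up survey stated | has had the intervention; survey not clearly stated | see Step 2 |

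An untreated randomised comparison exists up to month 3 and not at month 6.

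**Step 2. Does another reading rescue month 6?**

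- *Sections 4 and 6.1, 6-month survey for the intervention arm only.* No between-arm difference can be formed at 6 months. What remains is a within-arm change.
- *Summary and Section 6.2, surveys for every parent up to six months.* A difference can be formed, but waitlist parents have by then had the intervention.
- *Section 3.2.1, 6 months as the intervention length.* The waitlist arm still starts at 3 months, so it is still treated by month 6.

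No reading gives an untreated comparison at 6 months.

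**Step 3. Size of the 6-month contrast, for illustration**

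Let d be the benefit each arm gains by the end of its own three months, and f the fraction the intervention arm retains from month 3 to month 6. Both are assumed. Any trend shared by the arms cancels.

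- Month 3, intervention minus waitlist: d - 0 = d.
- Month 6, intervention minus waitlist: f·d - d = (f - 1)d.

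With d = 0.3 SD:

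- Month 3: 0.30 SD.
- Month 6, f = 1: (1 - 1) × 0.3 = 0 SD.
- Month 6, f = 0.5: (0.5 - 1) × 0.3 = -0.15 SD.

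A working intervention would show no difference or a reversed one.

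**Step 4. Precision of the 3-month contrast (optional note)**

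Assume equal arms, one follow-up and adjustment for a baseline with correlation r to follow-up. The 95% half-width in SD units is 1.96 × sqrt((2/n)(1 - r²)).

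| n per arm | r = 0 | r = 0.5 | r = 0.7 |
|---|---|---|---|
| 50 (no dropout) | 0.392 | 0.339 | 0.280 |
| 40 (20% dropout) | 0.438 | 0.380 | 0.313 |

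The 3-month difference would be known to about ±0.28 to ±0.44 SD.

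The pilot estimates the variance inputs better. For an RCT with 80% power, two-sided 5%, a fixed target of 0.3 SD and r = 0.5, n per arm = 2(1 - 0.25)(2.8016/0.3)² = 130.8, or 131. When the SD and correlation are estimated together from the same 80 parents, simulation puts the central 80% of that figure at about 103 to 156.

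**The case against.** **The untreated comparison is already in the design.** Both arms are surveyed monthly, and 8.4 models change over time by arm, so a contrast before the waitlist arm starts can be estimated as planned. This stands. A reader might infer that the pilot cannot estimate a treated-versus-untreated effect at all, and the documents do not support that. The defect is that the stated outcome time point is a different one and no section names the usable contrast.

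**No section commits to a 6-month between-arm difference.** Section 3.2.1 defines a change for each parent, and if only the intervention arm is surveyed at 6 months the difference cannot be computed. This also stands, so the -0.15 to 0 SD range is an illustration under one reading with assumed retention, not a forecast. If the benefit grew after month 3 (f above 1) the difference would be positive, but it would still not be the treated-versus-untreated effect.

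**A reader might infer that the raw point estimate will fix the RCT's sample size.** The plan does not say so. The parameter estimates in 8.4 may include variances, the mixed model yields standard errors, and the power analysis belongs to a later proposal that is not before us. Section 8.2 also admits low power for small differences. How that proposal treats uncertainty is a reasonable question for its authors, and silence on it here is not an error. Powering the RCT on a smallest worthwhile difference is one defensible method among several and should not be required of this plan.

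**Conclusion.** The point holds as a mismatch between purpose and time point. The plan promises effect sizes for an RCT, fixes its outcome at 6 months, and has no untreated arm at 6 months. This follows from the summary and Sections 3.2.1, 4, 6.1, 8.2 and 8.4 without any assumption, and the broader survey wording in the summary and Section 6.2 does not alter it.

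The size is illustrative. With an assumed gain of 0.3 SD in each arm and 50-100% retention, a 6-month arm difference would be -0.15 to 0 SD, against 0.30 SD at 3 months.

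The imprecision of about ±0.28 to ±0.44 SD (assumed correlation 0.7 to 0, dropout 0-20%) is a reason to show the interval beside the estimate. It is not a fault in a feasibility study of this size, and it does not show that the sample is too small for the study's purpose.

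The change should be made: a stated product of the trial depends on it, and the data are already planned.

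**What to change.** 1. In Section 3.2.1, the summary and Section 8.4, state: 'The between-arm effect estimate is the randomised, baseline-adjusted difference in the 8-item score at 3 months, measured before the waitlist arm starts the intervention, reported with its 95% CI. Change to 6 months is a within-arm description.'
2. Reconcile which arms are surveyed at 6 months (summary, Sections 4, 6.1 and 6.2).
3. Reconcile the statements on intervention length and on what 6 months represents (summary, Sections 3.2, 3.2.1, 4, 6.1 and 6.2). The investigators must decide which is intended.
4. Optional: in 8.4, say that the CI will accompany the point estimate in later power analyses, and give the expected precision with its assumptions.

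**Cost.** No new data collection, since monthly surveys in both arms already cover month 3. The stated primary time point changes, however, so an IRB-approved protocol must be amended, and the 6-month result becomes descriptive.

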8.3 Planned interim analyses (if applicable)

Not applicable.

8.4 Final analyses plan

We will use generalized linear mixed models to model change in parent attitudes and behaviors over time as a function of treatment arm and baseline characteristics. We will handle missing data on survey outcomes using multilevel multiple imputation. Parameter estimates generated from these secondary analyses will be used for refining the intervention and for power analyses in a subsequent grant proposal.

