6 STUDY INTERVENTION

6.1 Study intervention description

The BIPAS Alcohol intervention offers education and tools to parents of children ages 10-12 about preventing early onset alcohol use through information delivered via text message. Parents will receive text messages on early onset alcohol use, negative effects, and evidence-based recommendations about encouraging discussion and rules with their child about alcohol. Text messages will be delivered 2-3 times/week for three months.

Parents will complete a baseline survey as well as monthly surveys about alcohol-related beliefs, knowledge, and behaviors. Parents in the intervention group will also complete a follow-up survey six months after enrollment.

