6.2 Dosage, preparation, and administration of study intervention

Each parent will receive text messages up to three times weekly and monthly surveys from our study team for a period of up to six months.

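### Section 8.4 models change by a fixed arm label, with no time coding, window or crossover rule, although the waitlist arm starts texts at month 3, so the arm estimate need not measure texts versus no texts

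*Combined protocol and SAP*

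**What the plan says.** Exposure changes over the study. In section 4, "Parents in the intervention group will begin receiving the intervention after enrollment", whereas "parents in the waitlist-control group will receive the intervention three months after enrollment". Section 6.1 sets the duration: "Text messages will be delivered 2-3 times/week for three months".

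The primary change runs from baseline to month 6. Section 3.2.1 describes those six months as the length of the intervention, while the synopsis treats month 6 as post-intervention.

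The survey schedule after month 3 can be read in two ways. Section 4 says "Parents in both groups will complete monthly surveys, and their child will complete one survey after three months" and adds "The parents in the intervention group will also receive a follow-up survey at 6 months". Section 6.1 likewise names the six-month survey for the intervention group only. The synopsis, however, has parents "complete surveys for up to 6 months after study enrollment", and section 6.2 gives each parent "monthly surveys from our study team for a period of up to six months".

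The analysis plan in section 8.4 is one short paragraph. It names generalized linear mixed models that "model change in parent attitudes and behaviors over time as a function of treatment arm and baseline characteristics", with multilevel multiple imputation for missing survey outcomes. The resulting estimates are to refine the intervention and to size a later trial. Section 8.2 also makes effect-size estimation a purpose of the study.

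**The concern.** Treatment arm is fixed at randomisation, but what it stands for changes at month 3. In months 1-3 the arms differ as texts versus no texts. In months 4-6 they differ as texts finished versus texts in progress. An arm term that draws on both periods, or an arm contrast at month 6, therefore does not estimate the effect of the texts. Section 8.4 has no exposure term, restriction to the randomised period or named contrast that would prevent this.

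At stake is the effect size that the pilot hands on. An effective programme could look weak, inert or harmful, and a later trial could be sized on the wrong figure. The choice of time coding and window also stays open until the data have been seen.

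**Working it through.** There is no planned figure to reproduce: the sample size of 100 comes with no effect size, SD, alpha or power. The check is how the arm estimate behaves under the readings that the text allows.

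**Inputs from the documents.** Intervention-arm texts in months 0-3; waitlist texts from month 3 for three months (sections 4 and 6.1); monthly surveys, with the waitlist's last survey unclear (synopsis, sections 4, 6.1 and 6.2).

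**Assumptions.** E is the reduction in pro-sipping score after three months of texts, so positive means benefit. The waitlist gains the same E by month 6. The waitlist's month-3 survey precedes its first text. Onset is gradual (linear over three months) or immediate. The benefit is sustained, or half is lost by three months after texts end.

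**Reading 1: both arms surveyed monthly to month 6.** Let d be the arm difference (intervention minus waitlist) at month t. The arm-by-linear-time slope is Σ(t-3)d / Σ(t-3)², with Σ(t-3)² = 28 for t = 0 to 6. With balanced surveys this equals the random-intercept model's estimate.

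| Pattern | d at months 0-6 (units of E) | Mean, months 1-6 | Slope per month | Month 6 |
|---|---|---|---|---|
| Gradual, sustained | 0, 1/3, 2/3, 1, 2/3, 1/3, 0 | 3/6 = 0.50E | 0/28 = 0 | 0 |
| Gradual, half lost | 0, 1/3, 2/3, 1, 1/2, 0, -1/2 | 2/6 = 0.33E | -2.33/28 = -0.083E | -0.5E |
| Immediate, sustained | 0, 1, 1, 1, 0, 0, 0 | 3/6 = 0.50E | -3/28 = -0.107E | 0 |

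Not all of the shortfall in the mean comes from the swap. With gradual onset, months 1-3 alone average (1/3 + 2/3 + 1)/3 = 0.67E, so the swap takes 0.67E to 0.50E. With immediate onset it takes 1.00E to 0.50E.

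**Reading 2: waitlist surveyed to month 3 only; intervention arm at months 0, 1, 2, 3 and 6; gradual onset.** The waitlist slope is 0. In the intervention arm the mean survey time is 12/5 = 2.4 and Σ(t-2.4)² = 21.2.
- Sustained, values 0, 1/3, 2/3, 1, 1: slope 3.467/21.2 = 0.1635; times 3 months = 0.49E.
- Half lost, values 0, 1/3, 2/3, 1, 1/2: slope 1.667/21.2 = 0.0786; times 3 = 0.24E.
- Average arm difference with month as a factor: 0.67E in both cases, the same as in a months 0-3 analysis, because month 6 has no waitlist data to contrast. The swap does not dilute it.
- A month-6 arm contrast has no observed waitlist values; imputation would have to supply the whole waitlist side.

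**Arm by categorical month.** At month 3 only one arm has been exposed, so that contrast is 1.00E in every pattern under either reading. A linear model cut to months 0-3 gives 1.00E with gradual onset and 0.90E with immediate onset.

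**Illustrative consequence.** Assume a true standardised effect of 0.5, estimated as 0.25, with two-sided 0.05 and 80% power. By n per arm = 2(1.96 + 0.842)²/d², a later trial would be sized at 252 per arm instead of 63. In the pilot itself, assuming 50 per arm, power would be Φ(0.25 × √25 - 1.96) = 23.9% instead of Φ(0.5 × √25 - 1.96) = 70.5%.

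**The case against.** A reader might infer that section 8.4, as written, necessarily halves, cancels or reverses a real effect. The documents do not support that. The section does not specify linear time, a single pooled arm effect or use of the entire follow-up. Change over time by arm can equally mean arm by categorical month, and that model gives an unbiased month-3 contrast.

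A reader might also infer that waitlist surveys answered during treatment will enter as control data. That is possible but not established. The synopsis and section 6.2 give a maximum period, not a schedule. Sections 4 and 6.1 give the month-6 survey to the intervention group as an addition, which would be redundant if both arms were surveyed monthly to month 6.

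Two further points are fair. If the primary outcome became the between-arm change to month 3 and the model estimated that contrast, most of the problem would go; what would remain is the risk of a linear or pooled term over later data. And section 8.4 speaks of several estimates from analyses that it calls secondary, in a pilot that admits limited power, so no single arm coefficient is declared decisive.

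All of this limits the certainty of the bias. It does not supply the missing contrast. With the primary change at month 6, even a categorical model that follows the plan would report month 6, where the arm contrast is not texts versus no texts or has no observed waitlist data.

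**Conclusion.** The point holds as a failure of specification with a possible large bias, not as proof of a wrong model. The same sentence in section 8.4 allows an analysis that recovers E in full at month 3 and others that return 0.50E, nothing or the wrong sign, and nothing in the plan chooses between them. Which result occurs depends on the time coding, the waitlist survey schedule, the speed of onset and how long the benefit lasts. The first two are not settled in the documents, and the last two cannot be known beforehand. The figures are expected values without sampling error or dropout, and they rest on equal benefit in the two arms once each has had its texts.

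**What to change.** In section 8.4, enter survey month as categorical with arm-by-month terms. Take the randomised effect, and the effect size for the later trial, only from the arm contrasts at months 1-3, and name month 3 as the main one. Report waitlist data after month 3 as each parent's change from their own month-3 score, and the intervention arm's month-6 data as within-arm maintenance, with neither presented as a randomised comparison.

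Reconcile the month-6 endpoint, the stated length of the intervention and the waitlist survey schedule across the synopsis and sections 3.2.1, 4, 6.1 and 6.2.

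The cost is a few sentences, a few more model parameters and slightly less precision than a single pooled arm term. No new data or participants are needed.
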